# 4.5.9 Blood Samples for Whole Genome Sequencing or Whole Exome Sequencing

At participating sites, blood samples will be collected for DNA extraction to enable WGS or WES to identify variants that are predictive of response to study drug, are associated with progression to a more severe disease state, are associated with susceptibility to developing adverse events, can lead to improved adverse event monitoring or investigation, or can increase the knowledge and understanding of disease biology and drug safety. Research will be aimed at exploring inherited characteristics. The samples may be sent to one or more laboratories for analysis.

Collection and submission of blood samples for WGS or WES is contingent upon the review and approval of the exploratory research by each site's IRB/EC and, if applicable, an appropriate regulatory body. If a site has not been granted approval for WGS or WES, this section of the protocol (Section 4.5.9) will not be applicable at that site.

Genomics is increasingly informing researcher's understanding of disease pathobiology. WGS and WES provide a comprehensive characterization of the genome and exome, respectively, and, along with clinical data collected in this study, may increase the opportunity for developing new therapeutic approaches or new methods for monitoring efficacy and safety or predicting which patients are more likely to respond to a drug or develop adverse events. Data will be analyzed in the context of this study but may also be explored in aggregate with data from other studies. The availability of a larger dataset will assist in identification and characterization of important biomarkers and pathways to support future drug development.

For sampling procedures, storage conditions, and shipment instructions, see the laboratory manual.

Blood samples collected for WGS or WES are to be stored until they are no longer needed or until they are exhausted. However, the storage period will be in accordance with the IRB/EC -approved Informed Consent Form and applicable laws (e.g., health authority requirements).

Refer to Section 4.5.6 for details on use of samples after patient withdrawal, confidentiality standards for data, and availability of data from biomarker analyses.

# 4.5.10 Optional Samples for Research Biosample Repository

# 4.5.10.1 Overview of the Research Biosample Repository

The Research Biosample Repository (RBR) is a centrally administered group of facilities used for the long-term storage of human biological specimens, including body fluids, solid tissues, and derivatives thereof (e.g., DNA, RNA, proteins, peptides). The collection, storage, and analysis of RBR samples will facilitate the rational design of new pharmaceutical agents and the development of diagnostic tests, which may allow for individualized drug therapy for patients in the future.

Samples for the RBR will be collected from patients who give specific consent to participate in this optional research. RBR samples will be analyzed to achieve one or more of the following objectives:

- To study the association of biomarkers with efficacy or disease progression
- To identify safety biomarkers that are associated with susceptibility to developing adverse events or can lead to improved adverse event monitoring or investigation
- To increase knowledge and understanding of disease biology and drug safety
- To study drug response, including drug effects and the processes of drug absorption and disposition
- To develop biomarker or diagnostic assays and establish the performance characteristics of these assays

# 4.5.10.2 Approval by the Institutional Review Board or Ethics Committee

Collection, storage, and analysis of RBR samples is contingent upon the review and approval of the exploratory research and the RBR portion of the Informed Consent Form by each site's IRB/EC and, if applicable, an appropriate regulatory body. If a site has not been granted approval for RBR sampling, this section of the protocol (Section 4.5.10) will not be applicable at that site.

# 4.5.10.3 Sample Collection

The following samples will be stored in the RBR and used for research purposes and assay development, including, but not limited to, research on biomarkers related to satralizumab, diseases, or drug safety:

- Leftover blood, serum, plasma, PBMCs, and any derivatives thereof (e.g., DNA, RNA, proteins, peptides)
- Serum and plasma samples collected at baseline and subsequent visits for RBR

The above samples may be sent to one or more laboratories for analysis, which may include proteins, metabolites, and immune cell assessment and/or profiling. DNA samples may be used for the analysis of germline or somatic variants via WGS, WES, or other genomic analysis methods. Genomics is increasingly informing researcher's understanding of disease pathobiology. WGS and WES provide a comprehensive characterization of the genome and exome, respectively, and, along with clinical data collected in this study, may increase the opportunity for developing new therapeutic approaches or new methods for monitoring efficacy and safety or predicting which patients are more likely to respond to a drug or develop adverse events.

Data generated from RBR samples will be analyzed in the context of this study but may also be explored in aggregate with data from other studies. The availability of a larger dataset will assist in identification and characterization of important biomarkers and pathways to support future drug development.

For sampling procedures, storage conditions, and shipment instructions, see the laboratory manual.

RBR samples are to be stored until they are no longer needed or until they are exhausted. However, the RBR storage period will be in accordance with the IRB/EC approved Informed Consent Form and applicable laws (e.g., health authority requirements).

#### 4.5.10.4 Confidentiality

RBR samples and associated data will be labeled with a unique patient identification number.

Patient medical information associated with RBR samples is confidential and may be disclosed to third parties only as permitted by the Informed Consent Form (or separate authorization for use and disclosure of personal health information) signed by the patient, unless permitted or required by law.

Given the complexity and exploratory nature of the analyses of RBR samples, data derived from these analyses will generally not be provided to study investigators or patients unless required by law. The aggregate results of any conducted research will be available in accordance with the effective Sponsor policy on study data publication.

Data generated from RBR samples must be available for inspection upon request by representatives of national and local health authorities, and Sponsor monitors, representatives, and collaborators, as appropriate.

Any inventions and resulting patents, improvements, and/or know-how originating from the use of the RBR data will become and remain the exclusive and unburdened property of the Sponsor, except where agreed otherwise.

# 4.5.10.5 Consent to Participate in the Research Biosample Repository

The Informed Consent Form will contain a separate section that addresses participation in the RBR. The investigator or authorized designee will explain to each patient the objectives, methods, and potential hazards of participation in the RBR. Patients will be told that they are free to refuse to participate and may withdraw their consent at any time and for any reason during the storage period. A separate, specific signature will be required to document a patient's agreement to provide optional RBR samples. Patients who decline to participate will not provide a separate signature.

The investigator should document whether or not the patient has given consent to participate and (if applicable) the date(s) of consent, by completing the RBR Research Sample Informed Consent eCRF.

In the event of an RBR participant's death or loss of competence, the participant's samples and data will continue to be used as part of the RBR research.

# 4.5.10.6 Withdrawal from the Research Biosample Repository

Patients who give consent to provide RBR samples have the right to withdraw their consent at any time for any reason. After withdrawal of consent, any remaining samples will be destroyed or will no longer be linked to the patient. However, if RBR samples have been tested prior to withdrawal of consent, results from those tests will remain as part of the overall research data. If a patient wishes to withdraw consent to the testing of his or her RBR samples during the study, the investigator must inform the Medical Monitor in writing of the patient's wishes through use of the appropriate RBR Subject Withdrawal Form and must enter the date of withdrawal on the RBR Research Sample Withdrawal of Informed Consent eCRF. If a patient wishes to withdraw consent to the testing of his or her RBR samples after closure of the site, the investigator must inform the Sponsor by emailing the study number and patient number to the following email address:

[contact]

A patient's withdrawal from this study does not, by itself, constitute withdrawal of consent for testing of RBR samples. Likewise, a patient's withdrawal of consent for testing of RBR samples does not constitute withdrawal from this study.

# 4.5.10.7 Monitoring and Oversight

RBR samples will be tracked in a manner consistent with Good Clinical Practice by a quality-controlled, auditable, and appropriately validated laboratory information management system, to ensure compliance with data confidentiality as well as adherence to authorized use of samples as specified in this protocol and in the Informed Consent Form. Sponsor monitors and auditors will have direct access to appropriate parts of records relating to patient participation in the RBR for the purposes of verifying the data provided to the Sponsor. The site will permit monitoring, audits, IRB/EC review, and health authority inspections by providing direct access to source data and documents related to the RBR samples.

# 4.6 TREATMENT, PATIENT, STUDY, AND SITE DISCONTINUATION4.6.1 Study Treatment Discontinuation

Patients must permanently discontinue study treatment if they experience any of the following:

- Any medical condition that the investigator or Sponsor determines may jeopardize the patient's safety if he or she continues to receive study treatment
- Investigator or Sponsor determination that treatment discontinuation is in the best interest of the patient
- Pregnancy
- Malignancy
- Severe hypersensitivity or anaphylactic reaction to satralizumab
- GI perforation
- Unacceptable toxicity
- Significant non-compliance with protocol procedures
- Meets the discontinuation criteria in the risk mitigation and dose modification strategy (see Section 5.1)

Patients may need to permanently discontinue study treatment if they receive prohibited therapy.

The primary reason for study treatment discontinuation should be documented on the appropriate eCRF. Patients who discontinue study treatment prematurely will not be replaced.

It is important to distinguish between "withdrawal from treatment / discontinue treatment" and "withdrawal from study." Patients who withdraw from treatment should be encouraged to remain in the study for the full duration of the SFU.

Patients who discontinue study treatment during the DB period for any reason should continue with all remaining assessments defined in the protocol. However, patients who

are unwilling to return to the clinic for all assessments will be asked to complete an EOT visit within 4 weeks and a SFU visit 12 weeks *after* the final dose of study drug.

Patients who discontinue study treatment during the OLE period will be asked to complete the EOT visit within 4 weeks and *a* SFU visit 12 weeks *after* the final dose of study drug.

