# Management of Possible Hypersensitivity Reactions to Satralizumab

- SC injections should be administered at the study sites. Patients should stay in the clinic/hospital for at least one hour after study drug administration for the first five doses of study drug in order to receive treatment immediately in case anaphylaxis occurs. Study sites should have medications (e.g., corticosteroid, antihistamine, and epinephrine) and access to resuscitation facilities.
- Administration of the study drug outside of the study site might be allowed during the OLE period, from OLE Week 24 onward (see Section 4.3.2), if the investigator determines that it is appropriate.
- Patients and caregivers will be provided with emergency contact information by the site. Patients and caregivers should be instructed to recognize the signs and symptoms of hypersensitivity reactions and to seek immediate medical attention if the patient develops symptoms of acute hypersensitivity reactions. Patients and caregivers should confirm with the investigator whether treatment with study drug may be continued.
- If an anaphylactic reaction or other serious hypersensitivity reaction occurs, the study drug should be discontinued.
- For other hypersensitivity reactions, a decision to continue or discontinue treatment with satralizumab will be made by the investigator in consultation with the Medical Monitor, taking into account the benefits and risks.

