# Management of Patients with Malignancies

The study drug should be discontinued in patients with malignancies (with the exception of local basal or squamous cell carcinoma of the skin that is completely excised with free margins).

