# 5.2.2 Serious Adverse Events (Immediately Reportable to the Sponsor)

A serious adverse event is any adverse event that meets any of the following criteria:

- Is fatal (i.e., the adverse event actually causes or leads to death)
- Is life threatening (i.e., the adverse event, in the view of the investigator, places the patient at immediate risk of death)

This does not include any adverse event that, had it occurred in a more severe form or was allowed to continue, might have caused death.

Requires or prolongs inpatient hospitalization (see Section 5.3.5.11)

- Results in persistent or significant disability/incapacity (i.e., the adverse event results in substantial disruption of the patient's ability to conduct normal life functions)
- Is a congenital anomaly/birth defect in a neonate/infant born to a mother exposed to study drug
- Is a significant medical event in the investigator's judgment (e.g., may jeopardize the
  patient or may require medical/surgical intervention to prevent one of the outcomes
  listed above)

The terms "severe" and "serious" are not synonymous. Severity refers to the intensity of an adverse event (e.g., rated as mild, moderate, or severe, or according to National Cancer Institute Common Terminology Criteria for Adverse Events [NCI CTCAE]; see Section 5.3.3); the event itself may be of relatively minor medical significance (such as severe headache without any further findings).

Severity and seriousness need to be independently assessed for each adverse event recorded on the eCRF.

Serious adverse events are required to be reported by the investigator to the Sponsor immediately (i.e., no more than 24 hours after learning of the event; see Section 5.4.2 for reporting instructions).

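### Protocol Section 4.6.1 requires a permanent stop for any malignancy and for severe hypersensitivity, while Section 5.1 lets two of these patient types continue

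*Protocol*

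**What the plan says.** Protocol Section 4.6.1 introduces its list with "Patients must permanently discontinue study treatment if they experience any of the following". One entry is malignancy, with no qualification. Another is "Severe hypersensitivity or anaphylactic reaction to satralizumab". The last entry brings in the discontinuation criteria of Section 5.1.

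Section 5.1.1.2, under the management of possible hypersensitivity reactions, uses a different criterion: "If an anaphylactic reaction or other serious hypersensitivity reaction occurs, the study drug should be discontinued". It then adds: "For other hypersensitivity reactions, a decision to continue or discontinue treatment with satralizumab will be made by the investigator in consultation with the Medical Monitor".

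Section 5.1.2.2, under the management of patients with malignancies, says that study drug should be discontinued, "with the exception of local basal or squamous cell carcinoma of the skin that is completely excised with free margins".

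Section 5.2.2 states that severe and serious are not synonyms. Severity is intensity, and of a severe event it says that "the event itself may be of relatively minor medical significance", with a severe headache as the example. It also requires that the two be kept apart: "Severity and seriousness need to be independently assessed for each adverse event recorded on the eCRF".

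**The concern.** Section 4.6.1 and Section 5.1 cover the same two risks with different triggers. Where the triggers differ, one section orders a permanent stop and the other leaves room to continue. Nothing in the protocol says which section governs.

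One site could re-expose a patient after a reaction that 4.6.1 treats as an absolute stop. Another could withdraw a patient for good after an event that 5.1.2.2 exempts. Section 9.2 does not allow prospective requests to deviate from the protocol, so a site that continues a patient under 5.1 could be cited against 4.6.1 with no rule to settle the matter. The 4.6.1 list also applies through the open-label extension, where most of the exposure time falls.

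**Working it through.** No arithmetic applies. The check is to take each type of patient through both sets of rules.

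| Patient | Section 4.6.1 | Section 5.1 | Result |
|---|---|---|---|
| Anaphylactic reaction | Permanent stop | Stop | Agree |
| Hypersensitivity, severe and serious | Permanent stop | Stop | Agree |
| Hypersensitivity, serious but not severe | Not named, but caught by the last entry, which brings in the 5.1 criteria | Stop | Agree |
| Hypersensitivity, severe but not serious, not anaphylactic | Permanent stop | Investigator decides with the Medical Monitor | **Differ** |
| Hypersensitivity, neither severe nor serious | Not named | Investigator decides with the Medical Monitor | Agree |
| Local basal or squamous cell skin carcinoma, completely excised with free margins | Permanent stop | Exempt | **Differ** |
| Any other malignancy | Permanent stop | Stop | Agree |

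Three points of wording decide the two rows that differ.

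1. *Is a severe, non-serious reaction a real category here?* Yes. Section 5.2.2 separates the two attributes. In Section 5.3.3, Table 11 (for events that CTCAE does not list) makes Grades 4 and 5 automatically reportable as serious. A Grade 3 event must be reported as serious under its footnote only if it is assessed as a significant medical event. A Grade 3 reaction can therefore be severe without being serious.

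2. *Does the cross-reference at the end of the 4.6.1 list remove the difference?* No. It is one more entry in a list where any single entry is enough to stop treatment. It closes the serious-but-not-severe case, but it cannot relax the unqualified entries above it, and it does not import the exceptions in 5.1.

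3. *Does either document give an order of precedence?* None was found. The force of the wording also differs: 4.6.1 says that patients must stop permanently, while 5.1.1.2 and 5.1.2.2 say that study drug should be discontinued.

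The conflict runs in one direction only. In both rows 4.6.1 is the stricter text and 5.1 the more permissive.

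**The case against.** The best defence is that 4.6.1 is a summary that points to Section 5.1 for detail, and that a specific rule is ordinarily read as governing a general one. The skin-cancer exception looks deliberate: the general safety exclusion criteria (4.1.2.3) and the background text of 5.1.2.2 make a similar allowance for excised basal and squamous cell carcinoma. This is a plausible account of what the sponsor meant. It remains interpretation, because the protocol does not say it, and the section that would have to yield is the one with the mandatory wording.

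It is also fair to say that the hypersensitivity gap is narrow. Seriousness includes any significant medical event in the investigator's judgement, so many severe reactions would be serious too and would stop under both sections. Section 5.1.1.2 requires the decision to weigh benefits and risks with the Medical Monitor. Section 4.6.1 separately requires a stop for unacceptable toxicity and for conditions that may jeopardise safety. These safeguards limit the harm but do not make the two texts agree.

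A reader might infer that the sections order sites to do opposite things. They do not. Section 5.1.1.2 leaves the decision open, and 5.1.2.2 only lifts an instruction to stop. Neither directs continuation, and a site that stops such a patient under 4.6.1 breaches neither.

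**Conclusion.** The inconsistency is real and confined to two patient types: severe, non-serious, non-anaphylactic hypersensitivity, and completely excised local basal or squamous cell skin carcinoma. The conclusion assumes that 4.6.1 is read as written and that severe and serious carry the meanings given in Sections 5.2.2 and 5.3.3. It is an internal inconsistency in stopping instructions, worth correcting because it concerns named risks and is cheap to correct.

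Two stronger inferences are not supported.

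- *A patient count.* Section 1.4 reports injection reactions in 12.5% of satralizumab-treated patients in the earlier indication, and a reader might scale this to the present sample. Injection reactions include local injection-site reactions (Section 5.3.5.1), so they are not hypersensitivity. The figure also comes from studies with a median double-blind satralizumab exposure of about two years, against 24 weeks here. The documents give neither the share of reactions that are severe but non-serious nor any rate of skin carcinoma. The number affected cannot be estimated and is probably small.

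- *A distorted primary result.* A withdrawal for an adverse event is classed as study drug or condition related (SAP Section 4.2.1.2), so a reader might expect the ambiguity to reach the primary analysis. Such withdrawals follow treatment policy: observed scores are kept, and copy-reference imputation is used only where later data are missing. Section 4.6.1 asks patients who stop in the double-blind period to continue all assessments. With few patients involved, the effect on the primary estimate is negligible.

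**What to change.** Reconcile Section 4.6.1 with Sections 5.1.1.2 and 5.1.2.2:

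- use one term for the hypersensitivity criterion in both places, tied to the definitions in Sections 5.2.2 and 5.3.3;
- state one malignancy rule in both places, so that the exception appears in both or in neither;
- or, instead, add a sentence saying which section prevails where they differ.

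Which version stands is a clinical decision for the sponsor, and no view on it is given here. The cost is the wording of two list entries at the next amendment, or a clarification letter to sites. No new data, procedures or analyses are needed.

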# 4.6.2 Patient Discontinuation from the Study

Patients have the right to voluntarily withdraw from the study at any time for any reason. In addition, the investigator has the right to withdraw a patient from the study at any time.

Reasons for patient discontinuation from the study may include, but are not limited to, the following:

- Patient withdrawal of consent
- Study termination or site closure
- Adverse event
- The participant enrolls into another interventional clinical study in which an investigational treatment or approved therapy for investigational use is administered.
- Loss to follow-up
- Patient non-compliance, defined as failure to comply with protocol requirements as determined by the investigator or Sponsor

Every effort should be made to obtain a reason for patient discontinuation from the study. The primary reason for discontinuation from the study should be documented on the appropriate eCRF. If a patient requests to be withdrawn from the study, this request must be documented in the source documents and signed by the investigator. Patients who withdraw from the study will not be replaced.

